# PROTOCOL Biomedical Research Saint Louis University

Protocol Title:

Shear wave sonoelastography for the noninvasive evaluation of hepatic fibrosis in the pediatric population

\_\_\_\_\_

Page numbers from a sponsor's protocol/grant may be referenced in 2b and 2c.

b) List your research objectives (specific aims & hypotheses of the study).

Hypothesis: We hypothesize that shear wave sonoelastography (SWE) measurements will correlate with the histopathologic assessment of liver fibrosis in pediatric patients.

Specific Aims: To perform SWE on pediatric patients with known liver disease who undergo a liver biopsy within one month of the ultrasound exam in order to determine the accuracy of SWE in evaluating the various stages of liver fibrosis using the METAVIR histopathologic scale. As a control, we will perform SWE on patients without liver disease to establish baseline measurements in a normal liver.

#### Please save frequently

c) Describe the study design (e.g., single/double blind, parallel, crossover, control, experimental, observational, etc.). If the study is investigator-initiated, a timeline for individual subject recruitment, follow-up, and analysis for the study is required. Also, indicate if the subjects will be randomized.

The study design is a prospective single blind control experiment. Subject recruitment will be ongoing as patients who undergo routine liver biopsy in order to evaluate their liver disease will also undergo an ultrasound with sonoelastography. The minimum number of patients required in the test group in order to determine accuracy of the research test is 100. Study recruitment for patients without liver disease will be stopped once 100 patients are enrolled. An additional 8 months will be required for study analysis.

d) If subjects will be given placebo, please justify placebo use. \*?HELP?\*

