		ii.	N/A	Will the research only remain active for lo subjects?	ong-term follow-up of	
		iii.	Y	Are remaining research activities limited instructions above).	to data analysis only? (See	
		iv.	Ν	For studies that are closed to subject acc to be re-consented (to inform them about procedures, study risks, study personnel,	changes to study	
	v					
	•	-	•	red and needs to be re-initiated.		
	E	xplain	any re	esearch activities occurring during lapse in	IRB approval.	
2.	2. Date the study was initially approved by the IRB:					
3.	Approval date of p	12/05/2017				
4.	4. Total number of participants/records/specimens you are approved to enroll.				200	
5.	5. Total number of subjects that have given consent (verbal or written) to date.				181	
6.	Total number of su N/A).	ıbjects	that fa	ailed screening (if not applicable, state	9	
7.	Total number of pa	articipa	172			
8.	For multi-center st wide (SLU site plu	NA				
9.	For multi-center st site plus other site	udies, s).	numb	er of subjects enrolled study-wide (SLU	NA	
10.	Number of withdra	awals 1	rom tł	ne research and explanation/reasons for w	ithdrawals.	
	None					
11.	Description an	d num	ber of	:		

C-PROTOCOL	e-ı	PR	οт		OL
------------	-----	----	----	--	----

		Saint Louis Oniversity	
otocol 	Title:	Shear wave sonoelastography for the noninvasive evaluation of her pediatric population	oatic fibrosis i
	a)	Reportable Protocol Deviations/Violations since the last approval date:	
		NA	
	b)	Unanticipated Problems (UPs) since the last approval date: NA	
	c) consi:	Serious Adverse Events (SAEs) since the last approval date:Note: Information he stent with the cumulative table, which should also be attached in section #16.	re should be
12.		e there been any complaints about the research during the last year?	N
	IT y	es, please describe.	
13.	exa pa an pu	efly describe the progress of the study to date. Provide a status of participants in stample, where is the most recently accrued participant in terms of timeline in the stuticipants are in long-term follow-up, explain what this consists of in terms of data c d/or intervention. Provide any new information in regard to risks. Summarize or attacolications or presentations.	dy? If ollection ach

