	un tot wi	ere are 78 participants and 88 exams in the liver disease group. Within this group, usable due to using the linear probe; 5 exams are unusable because they were sc al of 10 patients had two exams – of which 5 exams were repeated since they were th the linear probe and they returned for another curved exam; another 5 were repe ey had a second biopsy performed. A total of 72 exams in the liver group have usa	reen fails. A e initially done eated becaus
	un tot	ere are 93 control patients and 95 control exams. Within the control group, 12 exa able to be used due to using the linear probe; 2 are unusable since they were scre al of 2 patients had a repeat exam since they came back after initially having an ex ear probe. A total of 79 exams in the control group have usable data.	en fails. A
	So	reen fails include those from patients who moved too much, who were too obese to age, or in whom the liver biopsy was not performed.	o obtain an
14.	ls t	here a Data Safety Monitoring (DSM) plan for this study?	
		Y No	
		Yes, a copy of the DSM report(s) for the last approval period is attached.	
		Yes, but a copy of the DSM reports(s) for the last approval period is not attac explain below.	ched. Please
15.	FD		
		A Regulated Studies Food and Drug Administration (FDA) Regulated Study, (i.e., involves drugs, N	

0 -Protoc	PROTOCOL Biomedical Research Saint Louis University	Protocol # 25138 [name]
Protocol Title:	Shear wave sonoelastography for the noninvasive evaluation of hepatic pediatric population	; fibrosis in the
a)	Have there been any changes in the FDA status of any drug or device used in the study? If yes, please explain:	
b)	Have any of the investigational drugs or devices used in this study received FDA approval? If yes, please explain:	
c)	Have any new alternative drugs or devices been approved for treatment of the study condition that may affect subjects willingness to participate? If yes, please explain:	
	Have current subjects been notified? Please explain:	
d)	Has there been a change in the standard care that may be considered as an alternative to the investigational drug or device or that would affect the original study design? If yes, please explain:	
	Have current subjects been notified? Please explain:	
e)	Is there any new information that might affect the risk/benefit ratio and the willingness of current study subjects to participate or to continue to participate in the research? If yes, please explain:	

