#### Not Applicable

X Yes, study requires RBR review

e	<del>)</del> -P	ROTOCOL	PROTOCOL Biomedical Research Saint Louis University		Protocol # 25138 [name]
Pro	otoc	ol Title:	Shear wave sonoelastography for the noninvasive er pediatric population	valuation of hepation	c fibrosis in the
	6.	the NIH GCP Training Registration may be FDAAA definition of ClinicalTrials.gov. 2) behavioral "Clinical require personnel or Registering may be definitions here. Cor registering on Clinica	quire registration on ClinicalTrials.gov, and/or is this p ng Requirement? (Select "Yes" if either apply) required if any of the following apply: 1) The project n an "Applicable Clinical Trial", which requires registration As of January 1, 2017, a new NIH policy mandated b Trials" to be registered on ClinicalTrials.gov. In addition In NIH "Clinical Trials" to take GCP training every three required for Journal Publication (ICMJE). Please revie intact the CTO at [contact] with que alTrials.gov and refer to the training page of the IRB w GCP Training requirements.	neets the on on iomedical and n, NIH policies years. 3) w relevant stions about	,
 8. S (incl a)	udé Ex	description of each gi	* * * Subject Population * * * space below, please detail the participants that you a oup requested) subjects. (For example $\geq$ 18 yrs to 90 yrs).	re requesting to re	cruit
b)	Nu		ojects to be accrued at SLU or SLU site (this includes a of the SLU PI).	all 200	
	par	ceeding the number lis ticipants are to be acc scribed in 3d.	sted here is a protocol violation. Prior IRB approval is protocol violation. Prior IRB approval is protocol. If applicable, this number should be consistent v	required if addition with your power an	al alysis
c)	Nu	mber of evaluable sub	pjects to be accrued study wide. *?HELP?*	200	
d)	ec co re: Cli mi Tl	conomically or educationsent for themselves) search, and 2) specify ick on hyperlinks to ac itigating risks. he study is specifically	opulations (minors, pregnant women and fetuses, neo onally disadvantaged, prisoners, adults temporarily or : 1) provide the rationale for the importance of includir the measures being taken to minimize risks to potent ccess SLU Guidelines containing additional considerat	permanently unab ng this population in ially vulnerable sub ions and strategies e elastography in d	le to n the ojects. s for etermining

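### The plan calls 100 test-group patients the minimum needed to determine accuracy, gives no basis for that number in the documents provided, and has reached data analysis with 78 participants and 72 usable exams

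*Combined protocol and SAP*

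**What the plan says.** Item 2(c) (study design) sets the size of the test group: "The minimum number of patients required in the test group in order to determine accuracy of the research test is 100". For controls it gives a stopping point instead: "Study recruitment for patients without liver disease will be stopped once 100 patients are enrolled".

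Item 8(b) gives 200 as the number of subjects to be accrued. Its printed instruction on agreement with the power analysis in 3(d) begins "If applicable, this number should be consistent". Item 8(c) also gives 200, for evaluable subjects "to be accrued study wide". Item 4 of the Continuing Review form repeats 200 as the number approved for enrolment.

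Item 3(d) plans ROC curves, scatter and box plots, and a p value for each METAVIR stage. It gives no alpha, power, target AUROC, precision or expected stage mix. It mentions neither confidence intervals nor how repeat exams are handled.

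On status, the Continuing Review question that begins "Are remaining research activities limited" (to data analysis only) is answered Y, and category 8(c) of the Expedited Paragraphs is marked to the same effect. Item 13 of that form reports "78 participants and 88 exams in the liver disease group". Ten of these patients had two exams: five were rescanned after a linear-probe exam, and five "had a second biopsy performed". The item concludes: "A total of 72 exams in the liver group have" usable data.

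**The concern.** The plan sets its own condition for answering its main question, calls it a minimum, and goes to analysis without meeting it. The documents provided do not compare the achieved count with 100, revise the 100, or say what the difference means for the accuracy claim.

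Because 100 comes without a derivation, a reader cannot tell what precision or power it was meant to buy, and so cannot judge how much was given up. This bears on the aim, which is accuracy across the stages of fibrosis. Dividing roughly 70 patients over F0 to F4 may leave few in some stages, and the protocol names avoided biopsies as a possible consequence of the results.

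**Working it through.** **1. Can 100 be reproduced?** No. The documents provided state no significance level, power, effect size, target AUROC, precision or stage distribution. Values near 100 arise under assumptions the plan does not make: 98 patients for a correlation of 0.28 (80% power, two-sided 0.05), or 97 for a proportion of 0.80 estimated to within ±0.08. Other choices give anything from 30 (correlation 0.5, 80% power) to 259 (correlation 0.2, 90% power).

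**2. Distinct patients behind the 72 usable exams** (inputs from Continuing Review item 13). Five of the ten repeats replaced an unusable linear-probe exam, so they add no second usable exam. The five re-biopsied patients may have two usable exams each. With *b* the number who do (0 to 5):

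- distinct patients = 72 − *b*, so 67 to 72.

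The count of linear-probe exams is lost from the text, but 88 − 5 screen fails − 72 = 11 is implied. Five of these were redone, leaving 6 patients with a linear exam only. Then 78 − 6 − 5 = 67 patients, and 67 + 5 = 72 exams, which is the lower end of the range. That end assumes one exam per screen-fail patient and both exams usable in all five re-biopsied patients.

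**3. Shortfall against 100.**

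- Enrolled: 100 − 78 = 22.
- Usable: 100 − 72 = 28, up to 100 − 67 = 33.

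**4. Do the counts reconcile?** Not fully.

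- Participants: 78 + 93 = 171, against 172 in item 7.
- Screen fails: 5 + 2 = 7, against 9 in item 6.
- Usable control exams: 95 − 12 − 2 = 81, against 79 stated.

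As a worst case for the concern, 181 people consented and 171 are placed in a group, leaving 10. Putting all 10 in the test group gives 78 + 10 = 88, still below 100. So the shortfall is secure, but its exact size is not.

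**5. Effect on precision.** If the stage mix is unchanged, standard errors scale as √(100/n):

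- n = 78: √(100/78) = 1.13
- n = 72: √(100/72) = 1.18
- n = 67: √(100/67) = 1.22

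**6. Illustration on the AUROC scale.** The AUROC (A) and the share positive are assumed, since the documents give neither. Patients are treated as independent. The Hanley–McNeil variance is

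[A(1−A) + (n₁−1)(Q₁−A²) + (n₀−1)(Q₂−A²)] / (n₁n₀), with Q₁ = A/(2−A) and Q₂ = 2A²/(1+A).

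Worked case, A = 0.85 and 10% positive: Q₁ = 0.7391, Q₂ = 0.7811, A² = 0.7225.

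- n = 100 (10 and 90): (0.1275 + 0.1497 + 5.2137)/900 = 0.00610; SE 0.0781; half-width 1.96 × 0.0781 = 0.153.
- n = 67 (6.7 and 60.3): (0.1275 + 0.0948 + 3.4739)/404.01 = 0.00915; SE 0.0956; half-width 0.187.

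95% half-widths for A = 0.75 / 0.85 / 0.95:

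| n | 10% positive | 40% positive |
|---|---|---|
| 100 | 0.181 / 0.153 / 0.095 | 0.101 / 0.082 / 0.049 |
| 78 | 0.205 / 0.174 / 0.108 | 0.115 / 0.093 / 0.056 |
| 72 | 0.214 / 0.181 / 0.113 | 0.120 / 0.097 / 0.058 |
| 67 | 0.222 / 0.187 / 0.117 | 0.124 / 0.101 / 0.060 |

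Within any one scenario the loss against 100 is about 0.01 to 0.02 at n = 78, 0.01 to 0.03 at 72 and 0.01 to 0.04 at 67. The share positive and the assumed AUROC move the half-width far more than the shortfall does.

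**The case against.** **No power analysis was owed.** The prompt at 3(d) asks for sample size and power only from full-board studies without funding, and the application lists university, industry and foundation sources, some still at application stage. Item 8(b) is conditional as well. This stands, and no breach of the form is alleged. What remains is that the plan chose to state a required minimum.

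**The basis may lie elsewhere.** Item 2(c) may refer to a sponsor's protocol or grant, and the attachments were not available. This also stands, so the claim is limited to the documents provided.

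**The 100 must mean usable patients.** A reader might infer this by taking the 100 controls from the 200 evaluable subjects in 8(c). The documents do not support that inference. The control stop counts patients enrolled, not evaluable, and 200 is also the accrual figure in 8(b) and the approved enrolment, so 100 enrolled plus 100 enrolled fits equally well.

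**Accrual is an outcome, not a design fault, and the counts were reported openly.** This is fair. Item 13 asks for progress, not for a comparison with target. The comparison still has to be made in the analysis plan and the report.

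**The missing intervals and repeat-exam rule are separate matters.** This is correct. Both would be missing with 100 patients too, and neither follows from the shortfall.

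**Conclusion.** The plan states a required size, gives no basis for it in the documents provided, and does not reach it on either reading. The shortfall is about 22 enrolled patients, or about 28 to 33 with usable data. The usable figure depends on item 13's repeat counts being right. Reassigning every unplaced consent does not remove the enrolment shortfall.

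The cost in precision is modest: standard errors are about 13% to 22% larger than at 100 for an unchanged stage mix. A reader might infer that the study can no longer answer its question. The documents do not support that: with no stated precision target there is nothing it demonstrably fails to reach, and a loss of about 0.01 to 0.04 in AUROC half-width under the assumed scenarios does not make it uninformative. This should be fixed in the analysis plan and the report.

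**What to change.** 1. Keep the planned 100 on record. State its basis and whether it meant enrolled or usable patients, or state that no basis was derived.
2. State in the analysis plan and in the report that it was not reached.
3. Count from the data, and report separately, the distinct patients and the exams, overall and for each METAVIR stage. Reconcile the totals in the Continuing Review form while doing so.
4. As a related improvement that does not depend on the shortfall, give each ROC result a 95% confidence interval computed by patient, either by resampling patients in a bootstrap or by using one exam per patient under a stated rule. Up to five patients may contribute two usable exams. Limit stage-level accuracy claims to what those intervals support, since p values by stage will not show the precision achieved.

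The cost is a less favourable stated sample size, one table of counts and a little analysis work. No further enrolment is needed.

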#### 3. Study Procedures

a) N Is this project a multicenter study (i.e., same project is conducted elsewhere by a different investigator) OR does this study involve conduct of research at multiple sites?

Is SLU acting as a coordinating center for other sites OR is the SLU PI a direct recipient of a federal grant for this research? If yes, complete and attach the Supplemental Application for Coordinating Center Activities.

Will the SLU site be participating in all parts/procedures/arms of the study?

#### If No, explain what SLU will NOT participate in:

# Please save frequently

Page numbers from a sponsor's protocol/grant may be referenced in 3b, 3c, and 3d.

b) Describe all the procedures, from screening through end-of-study, that the human subject must undergo in the research project, including study visits, drug treatments, randomization and the

# PROTOCOL Biomedical Research Saint Louis University

Protocol Title:

Shear wave sonoelastography for the noninvasive evaluation of hepatic fibrosis in the pediatric population

which are standard o	art of standard of care. Specify whi care. Please note: The box below tach those files in the Attachment s	is for text only. If you would like
be performed as sta abdominal ultrasoun consent will then be patient for the perfor study. The research standard of care ultra liver biopsy. No add would normally have Following the liver bi complete. The patie	(0-18 years of age) with known live dard of care to assess the degree d to evaluate the liver. The ultrason obtained from the patient's parent of ance of a shear wave sonoelastog portion of the ultrasound exam wil asound exam. The ultrasound mus tional visits or treatments are requi as part of their routine treatment of opsy and ultrasound exam, the pati- nt's electronic medical record will b history, laboratory values, and live	of fibrosis will also undergo an and is also standard of care. In or guardian with verbal assent fr raphy exam as part of the resea I be performed at the same time t be performed within 1 month of red of the patients beyond what r medical care following the live ents involvement in the study is e reviewed for pertinent clinical
cholestasis, Alagille deficiency, progress fructosemia, Wilson	s include but are not limited to bilia syndrome, Caroli's disease, choled ve familial intrahepatic cholestasis disease, cystic fibrosis, autosomal i rico-caval shunt, post liver transpla	ochal cyst, alpha-1-antitrypsin (PFIC), viral hepatitis, glycoger ecessive polycystic kidney dise
ultrasound as standa whom the US shows asked to enroll in th completion of the ex	atric patient (0-18 years of age) und rd of care for evaluation for a diagr a normal liver, gallbladder, pancres e research study by undergoing she am, the patient's involvement in the its or study visits are required. Live	nosis other than liver disease ar as, spleen, and biliary tree will t ear wave elastography. Followi study will be complete. No add
pediatric gastroenter also be obtained. The	tained as random sample, preferate ologists as this is the area that the is should reduce sampling error an hin 1 month of the ultrasound exampling	sonoelastography measuremer d result discordance. The liver
systems by patholog of the standard of ca patient's chart will be Ishak:	aluation will be performed using the sts blinded to elastography results re evaluation of the biopsy material reviewed as part of the study.	These classifications systems
2: Fibrous expansion 3: Fibrous expansio 4: Fibrous expansio portal to central (P-C 5: Marked bridging ( 6. Cirrhosis, probab METAVIR:	P-P and/or P-C) with occasional nc	ut short fibrous septa nal portal to portal (P-P) bridgin ng [portal to portal (P-P) as we
F0: no portal fibrosis F1: portal fibrosis wi F2: portal fibrosis wi F3: portal fibrosis wi F4: cirrhosis		;

## PROTOCOL Biomedical Research Saint Louis University

\_\_\_\_\_

Protocol Title:

Shear wave sonoelastography for the noninvasive evaluation of hepatic fibrosis in the pediatric population

Shear wave ultrasound—Using 2 probes (C1-6 which is a low frequency curved probe and L9 which is a high-frequency linear probe) on the the GE Logiq E9, the selected area of interest (ROI) will be in the right lobe of the liver or in a portion of a transplant liver. The ROI will be an area away from vessels and bile ducts using an intercostal or subcostal approach. Ten separate acquisitions will be obtained on each patient by the attending radiologist and sonographer who are blinded to the results of the liver biopsy. The mean value will be used.

- c) If the proposed study is a clinical trial where a drug, vaccine, device or other treatment is compared to a placebo group or comparison treatment group, what are the guidelines or endpoints by which early decisions regarding efficacy or lack of efficacy can be made? For example, it may be reasonable to stop enrollment on a study when efficacy has already been clearly demonstrated, to avoid unnecessary enrollments of additional subjects. Alternatively, it may be reasonable to stop enrollment when it is clear that efficacy will never be demonstrated, given the statistical power of the study as designed. Describe the guidelines that are in place to assist in making these determinations, if relevant to the proposed study.
- d) Describe how data analysis will be performed (statistical tests, methods of evaluating data) and indicate the smallest group/unit for which separate reporting will occur. For studies involving a questionnaire, if data and reliability information are available, please describe or provide references. For full board, unfunded studies describe sample size determination and power analysis. If none, please justify.

The results of the SWE using the velocity measurements displayed on the elastography map with a quantitative color map that is expressed in kPa (kiloPascals) will be correlated with the stage of fibrosis using the METAVIR scale from the liver biopsy results in order to determine the accuracy of SWE in evaluating the various degrees of liver fibrosis. The statistical analysis will include Receiver Operating Characteristic curves as well as scatter plots and box plots. The mean and median values as well as a range of the SWE measurements will be correlated with the individual METAVIR stages of fibrosis (F0-F4), and a p value will be calculated for each stage to assess the accuracy of SWE based on individual fibrosis stages. Further statistical analysis will also be performed to compare results of SWE and histopathology in subgroups of liver disease patients, such as those with NASH compared to those without. Scatter plots will be used to compare the SWE results in normal patients to those with liver disease.

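### Section 3(d) does not make the planned SWE–METAVIR correlation the primary test and adds five unadjusted stage p values plus open-ended subgroups: about a 20% chance of a false stage result at an assumed 0.05

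*Combined protocol and SAP*

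**What the plan says.** The hypothesis in section 2(b) is that SWE "measurements will correlate with the histopathologic assessment of liver fibrosis in pediatric patients". The specific aim beside it is to determine how accurately SWE evaluates the METAVIR stages.

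Section 3(d) opens by planning to correlate SWE with METAVIR stage, and it lists ROC curves, scatter plots and box plots. It continues: "The mean and median values as well as a range of the SWE measurements will be correlated with the individual METAVIR stages" (F0 to F4), and "a p value will be calculated for each stage to assess the accuracy of SWE based on individual fibrosis stages". It then adds comparisons of SWE and histology "in subgroups of liver disease patients, such as those with NASH compared to those without".

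Section 3(b) fixes the value taken from the ten acquisitions on each patient: "The mean value will be used".

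The protocol does not name a primary analysis, correlation coefficient, significance level, comparator for the stage p values, ROC cut-point, multiplicity rule or closed list of subgroups. Section 2(c) gives a minimum of 100 test patients, with no calculation behind it.

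**The concern.** The plan has one hypothesis and several results that could be offered in answer to it. The correlation in the first sentence of 3(d) is the natural test, but nothing gives it priority. The only p values the plan commits to are the stage-by-stage ones. If F1 and F4 came out significant and F0, F2 and F3 did not, the plan would give no verdict on 2(b).

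Two things follow. The family of stage tests has no controlled error rate, and an open subgroup list lets that family grow after the data are seen. The stages are also ordered, so testing them one at a time ignores the trend that the hypothesis is about. The lay summary in 2(a) says SWE may remove the need for biopsy in these children. A claim of that weight should rest on a result chosen in advance.

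**Working it through.** **The plan's own figure.** The minimum of 100 in 2(c) can be neither reproduced nor refuted, because no alpha, power, effect size or precision target accompanies it.

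**Inputs from the documents.** Five stages with one p value each (3(d)). Three summaries named (3(d)), with the mean as the working value (3(b)). 72 usable liver-group exams, from 78 participants and 88 exams (continuing review form, progress item).

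**Assumptions.** Two-sided 0.05 per test. Each stage compared with all other stages by a Mann-Whitney test. No true relation between SWE and stage.

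**Number of tests.** 5 × 1 = 5 on the direct reading. 5 × 3 = 15 if each summary is tested separately.

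**If the tests were independent**, the chance of at least one false positive is 1 − 0.95^k:
- k = 5: 1 − 0.7738 = 22.6%
- k = 6: 26.5%
- k = 10: 40.1%
- k = 15: 1 − 0.4633 = 53.7%

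**Allowing for correlation.** The tests share the same children, and mean and median come from the same ten acquisitions, so the independent figures are too high. Null simulations give the following.

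| Tests | Independent | Simulated, normal data | Simulated, lognormal data |
|---|---|---|---|
| 5 stages, mean only | 22.6% | 20.4–21.4% | 19.4–22.1% |
| 5 stages + one NASH comparison | 26.5% | 24.6–25.6% | not run |
| 10: mean and median | 40.1% | 22.6–25.2% | not tabulated |
| 15: mean, median, each child's range | 53.7% | 38.1–40.7% | 32–37% |

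The normal-data runs used 3,000 replicates per scenario: 72 exams with equal or skewed stage mixes, or 100 exams with equal stages. Within-patient SD was 0.5 or 1.0 times the between-patient SD, and NASH prevalence was assumed to be 40%. The lognormal runs used 72 exams and single-acquisition ICCs of 0.6 and 0.8. The five-test result barely moves with sample size, stage mix or distribution. The fifteen-test result depends on the distribution assumed, and most of its excess comes from testing each child's range.

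**Another comparator.** Four cumulative cut-points (≥F1 to ≥F4) on the mean give about 14–16%.

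**After the fix.** One primary test at 0.05 gives about 5%. If the five stage p values are kept, Holm compares the smallest with 0.05/5 = 0.01, the next with 0.05/4 = 0.0125, and so on, which holds the family at 5% or below.

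**Exams versus children.** 88 − 78 = 10 repeat exams. Five replaced linear-probe scans and five followed a second biopsy. At most five children can therefore contribute two usable exams, so the 72 exams come from at least 72 − 5 = 67 children.

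**The case against.** The strongest reply is that the right analysis is already in the plan. The opening of 3(d) correlates SWE with METAVIR stage, and 3(b) fixes the mean as the value. What is missing is a coefficient, an alpha, an interval and the word primary. That is correct, and it is why the fix promotes an existing analysis instead of inventing one.

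A second reply is that the plan never says any single p < 0.05 supports the hypothesis. The stage p values are given another purpose, assessing accuracy stage by stage. This also stands. The 20% is the chance of at least one false stage result. It is not the error rate of a decision rule that the protocol adopts.

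A reader might go further and infer that a false significant finding is likely, or that fifteen p values are planned. The documents do not support either. No simulated figure reaches one half; only the independence figure for fifteen tests does, and these tests are correlated. The commitment is that "a p value will be calculated for each stage", which is five. Beside box plots, mean, median and range read most naturally as descriptions of each stage.

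Finally, the aim is accuracy, where ROC estimates with intervals matter more than p values. That is fair, but several AUCs with no named cut-point would also leave no primary result.

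**Conclusion.** The point holds in a limited form. Section 3(d) contains the correlation that would test 2(b) but does not make it primary, and it surrounds it with five unadjusted stage p values and an unbounded set of subgroup comparisons. At an assumed two-sided 0.05, with one-stage-versus-rest tests, the chance of at least one false stage result is about 20%, four times nominal. One NASH comparison takes it to about 25%. The 32–41% range applies only if all three summaries are tested separately. A cumulative cut-point comparator would give about 14–16%. All these figures rest on an alpha and a comparator that the plan does not state. The absence of a primary result does not depend on those assumptions.

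**What to change.** In section 3(d):

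- Make the planned correlation the single primary analysis: Spearman or Kendall tau-b between mean SWE and METAVIR F0–F4 in biopsied children, two-sided 0.05, with a 95% CI.
- Use one pre-specified exam per child, for example the first usable exam–biopsy pair, so that children with a second biopsy count once.
- Report mean, median and range by stage descriptively, or Holm-adjust the five stage p values if they are kept.
- Label NASH and other subgroup comparisons exploratory and give estimates with CIs.
- Keep the ROC curves as the accuracy estimates.
- Date the change and state which results had already been seen. The continuing review form says only data analysis is left, and the attachments list (section 16) includes a 2017 meeting submission with figures and a table, attached in December 2016.

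The cost is one paragraph, with no new patients or data. Power need not suffer: in simulation with 72 exams and an assumed rise of 0.3 SD per stage, a Spearman test had 89–94% power under the two stage mixes tried. That figure depends on the assumed effect and treats the 72 exams as independent children. The downsides are that stage and subgroup p values can no longer be presented as confirming the hypothesis, and that a primary test named at this point may not be fully prospective.
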